#### 4.2. Study Rationale

As noted above, although Sentinel was approved by FDA for capturing debris during TAVR, the pivotal RCT missed its primary endpoint. In the same trial, post hoc analysis showed clinical benefit with reduction in procedural stroke. However, prospective data to prove clinical benefit are lacking. The objective of the PROTECTED TAVR study is to demonstrate that use of Sentinel significantly reduces the risk of peri-procedural stroke ( $\leq 72$  hours) after TAVR.

[figure not shown]
### 5. Commercial Device Description (part of Standard of Care)

The Sentinel® Cerebral Protection System is indicated for use as a cerebral protection device to capture and remove embolic material while performing transcatheter aortic valve procedures in order to reduce ischemic injury to the brain peri-procedurally.

#### 5.1. Overview of the Sentinel® Cerebral Protection System

[figure not shown]
The commercially available Sentinel Cerebral Protection System (Sentinel; Boston Scientific Corporation, Marlborough, MA, USA) is designed to capture and remove debris dislodged during endovascular procedures. It consists of 2 filters within a single 6-F delivery catheter percutaneously placed from the right radial or brachial artery over a 0.014-inch guidewire.

The major features of the system are shown in **Figure 5.1-1**. The articulating sheath tip, proximal sheath tip, proximal filter hoop, proximal articulating sheath marker, distal filter hoop and distal filter tip are radiopaque to enable visualization during use. The filters are positioned in the brachiocephalic artery (proximal filter) and the left common carotid artery (distal filter) before the TAVR procedure (**Figure 5.1-2**) and are withdrawn into the catheter and removed after TAVR. Additional product information can be found in the commercial Instructions For Use (IFU).

**Figure 5.1-1: Diagram of the Sentinel System**

The pore size of the filters is 140 µm.

**Figure 5.1-2: Positioning of the Sentinel Device**

The proximal filter is placed in the brachiocephalic artery and the distal filter is placed in the left carotid artery.

## 5.2. *Device Labeling*

A basic description of the device and a comprehensive set of instructions (IFU) are contained in each product package.

## 6. Study Objectives and Endpoints

### 6.1. *Study Objectives*

The objective of the PROTECTED TAVR study is to demonstrate that use of the Sentinel® Cerebral Protection System significantly reduces the risk of peri-procedural stroke ( $\leq 72$  hours) after transcatheter aortic valve replacement (TAVR).

### 6.2. *Study Endpoints*

Outcomes will be assessed on an intention-to-treat (ITT) basis and on a per-protocol basis. The ITT analysis set includes all subjects who sign an Informed Consent Form (ICF; see Section 20) approved by the Institutional Review Board (IRB)/Independent Ethics Committee (IEC)/Human Research Ethics Committee (HREC) and are enrolled upon randomization (see Section 9.1 for point of enrollment), whether or not the assigned treatment is received. The Per-Protocol analysis set includes all ITT subjects who receive the assigned treatment (excludes crossovers).

#### 6.2.1. **Primary Endpoint**

The primary endpoint is all stroke (hemorrhagic, ischemic, or undetermined status) through 72 hours post TAVR procedure or discharge (whichever comes first) as adjudicated by an independent Clinical Events Committee (CEC) and using Neurologic Academic Research Consortium (NeuroARC) definitions.

The primary analysis set for the primary endpoint is the ITT analysis set.

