**Table 6.3-1: Overview of Objectives and Endpoints**

Objective	Endpoint	Rationale for Endpoint
Primary Endpoint		
Evaluate effectiveness of the cerebral protection device during TAVR procedures	All stroke to 72 hours post-TAVR procedure	Demonstrate significant reduction of peri-procedural stroke (≤72 hours) after TAVR, which is a critical acute safety event observed in the population undergoing TAVR.
Additional Measurements of Safety and Effectiveness		
Evaluate safety of the cerebral protection device	Safety measures peri- and post- TAVR procedure and at discharge	Confirm safety based on assessments recommended by VARC  and NeuroARC  for this elderly population.

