### 10.6. *Post-Procedure (≤ 72 Hours)/Prior to Hospital Discharge*

Within 72 hours post TAVR procedure or before discharge (whichever comes first), the following neurological assessments must be performed (see **Note 1** below).

- Neurological physical exam (see **Note 2** in Section 10.4 and **Note 2** below)
- mRS score (see **Note 2** in Section 10.4 and **Note 2** below)
- NIHSS score (see **Note 2** in Section 10.4 and **Note 2** below)
- CAM-ICU (see **Note 3** in Section 10.4 and **Note 3** below)
- MoCA (see **Note 4** in Section 10.4)

**Note 1:** Follow-up neurological assessments must be performed within 72 hours post TAVR procedure but may be performed earlier if deemed necessary. These post-procedure assessments should be performed only when the subject is no longer drowsy from procedural medication. The neurological assessor should be blinded to the subject's cerebral protection device treatment group.

**Note 2:** In all subjects where stroke is suspected, a formal neurology/stroke consult should be obtained, and the subject should be further assessed and treated per standard of care. In subjects diagnosed with post-procedural stroke, mRS must also be administered at 30±7 days following the stroke (see Section 10.7 below). The simplified mRS questionnaire may be used for this follow-up assessment.

**Note 3:** This delirium assessment should be done on day 1 post TAVR procedure.

A complete safety event assessment, including any SAE, ADE, SADE, UADE, USADE, device deficiency with associated treatment, and any CEC event regardless of seriousness and device relationship (see Section 19) must be carried out and reported to BSC from the time of enrollment through 72 hours post TAVR procedure or subject discharge (whichever

comes first). Please see Section 10.7 below for additional information regarding subjects with stroke.

The subject may be discharged from the hospital when clinically stable, at the Investigator's discretion per local standard of care. Pharmacologic management of subjects in both treatment groups, including antiplatelet and anticoagulant medications, is left to the discretion of the treating physician.

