### 10.8. *Study Completion*

All subjects will be followed through 72 hours post TAVR procedure or hospital discharge (whichever comes first). A subject's participation in the study will be considered complete after 72 hours or hospital discharge (whichever comes first). See Section 10.7 regarding additional follow-up for subjects who experience a stroke. For those subjects, study duration will be through 30±7 days after the stroke.

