##### 11.1.1.1. Statistical Hypothesis for the Primary Endpoint

The primary statistical hypothesis is that the rate of the primary endpoint (all stroke through 72 hours post TAVR procedure or discharge [whichever comes first]) in the Sentinel (Test) cohort is superior to that in the Control cohort. The null and alternative hypotheses for the primary endpoint are as follows:

$$H_0: P_{\text{Sentinel}} = P_{\text{Control}}$$

$$H_1: P_{\text{Sentinel}} \neq P_{\text{Control}}$$

where  $P_{\text{Sentinel}}$  and  $P_{\text{Control}}$  correspond to the rates of the primary endpoint for the Sentinel cohort (test) and the Control cohort (no cerebral protection), respectively.

Testing will be done for the primary endpoint as described in the statistical analysis plan. A chi-square test will be used. The primary analysis population for the primary endpoint is the ITT analysis set; this endpoint will also be analyzed for the Per-Protocol analysis set (see Section 11.2.1 for description of analysis sets).

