##### 11.1.1.2. Sample Size Parameters for the Primary Endpoint

The sample size parameters for the primary endpoint are shown below.

- Expected Control rate  $P_{\text{Control}}$ : 4%
- Expected Sentinel (test) rate  $P_{\text{Sentinel}}$ : 2% (50% relative reduction)
- Test significance level ( $\alpha$ ): 0.05 (2-sided)
- Power ( $1 - \beta$ ): > 0.90 (see **Note 1** below)
- Test to Control ratio: 1:1 (see **Note 2** below)
- Number of evaluable subjects: up to 6000 maximum enrollment with sample size re-estimation
- Planned enrollment: = 3000 subjects (N=1500 per cohort)

The statistical approach uses an adaptive group sequential design. There will be 1 planned formal interim analysis performed on the first 70% of enrolled subjects (N=2100) by the Independent Safety and Statistical Monitor (see Section 21.3). The study will be stopped if a significant difference in favor of the test arm is observed after this interim analysis.

Based on the results of the interim analysis, sample size re-estimation may be performed and the sample size may be increased up to a maximum of 6000 subjects. Details of this adaptive approach are pre-specified in the Independent Safety and Statistical Monitor charter. A final analysis will be performed on all enrolled subjects if the study is not stopped after the interim analysis (see Section 11.1.1.3 and Section 11.3.2 below).

**Note 1:** This power calculation includes sample size re-estimation.

**Note 2:** Randomization will occur at the index procedure (prior to procedural puncture/incision) to avoid selection/treatment bias.

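### Does ending the primary endpoint at hospital discharge undercut the 72-hour stroke objective?

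*Combined protocol and SAP*

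**What the plan says.** Section 6.1 sets out to show that the device "significantly reduces the risk of peri-procedural stroke", with 72 hours as the stated limit. Table 6.3-1 lists the primary endpoint as "All stroke to 72 hours post-TAVR procedure". Neither mentions discharge.

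Section 6.2.1 defines the endpoint as all stroke "through 72 hours post TAVR procedure or discharge (whichever comes first". The synopsis and Sections 11.1.1, 11.1.1.1, 11.1.1.3 and 11.3.2 use the same limit. Under Section 10.8 a subject's "participation in the study will be considered complete after 72 hours or hospital discharge (whichever comes first"; only subjects with a stroke are followed further.

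Section 10.6 leaves discharge to the investigator under local standard of care: "The subject may be discharged from the hospital when clinically stable". The same section requires a full set of neurological assessments before discharge or 72 hours, and says of the person doing them: "The neurological assessor should be blinded".

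For the analysis, Section 11.1.1.1 says "A chi-square test will be used". Section 11.1.1.2 plans for 4% in Control and "2% (50% relative reduction" in the Sentinel arm, with 1500 subjects per arm and power above 0.90 including sample size re-estimation.

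**The concern.** A stroke at 60 hours in a subject who went home at 36 hours falls within the objective and Table 6.3-1 but not within the endpoint. The length of observation is fixed after randomisation by a treating team that knows the assignment. A chi-square test takes no account of observation time. Stratifying by center balances local discharge habits but not a difference between arms within a center. The analyses named for the primary endpoint are ITT, Per-Protocol, subgroups by operative risk and gender, and poolability; none uses discharge time.

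Three things would be at stake: a claim wider than the data, power lower than stated if 4% and 2% were full 72-hour rates, and a distorted comparison if one arm were discharged sooner.

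**Working it through.** **1. Which wording governs.**

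| Place | Discharge limit stated? |
|---|---|
| Objective, Section 6.1 (also Sections 2, 4 and 4.2) | No |
| Table 6.3-1 | No |
| Endpoint, Sections 6.2.1 and 11.1.1 | Yes |
| Hypothesis, Section 11.1.1.1 | Yes |
| Success criterion, Section 11.1.1.3 | Yes |
| Interim rule, Section 11.3.2 | Yes |

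Table 6.3-1 is introduced as an overview of endpoints already given. Everything that determines what is counted, tested and concluded carries the limit.

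**2. Which window the planning rates refer to.** Section 11.1.1.1 defines P_Control and P_Sentinel as rates of the primary endpoint. Section 11.1.1.2 uses the same symbols under a heading naming that endpoint. So 4% and 2% are rates to 72 hours or discharge. Section 4.1 fits this but does not prove it: its unprotected rates at up to 72 hours are 8.2% and 5.44%, both above 4%, and its relative reductions are 63% and 65%, both larger than 50%.

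**3. The plan's own figures.** Inputs: two-sided alpha 0.05, interim at 70%, 1050 then 1500 per arm, 4% versus 2%.

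- Interim, Lan-DeMets spending of O'Brien-Fleming type, per side: 2[1 − Φ(2.2414/√0.7)] = 2[1 − Φ(2.679)] = 0.00738. Doubled, this is 0.0148.
- Final: solving the bivariate normal with correlation √0.7 gives z = 2.000, so 0.0455. Both match.
- Final-look power: pooled SE = √(2 × 0.03 × 0.97/1500) = 0.006229; unpooled SE = √((0.04 × 0.96 + 0.02 × 0.98)/1500) = 0.006218. Power = Φ[(0.02 − 2.000 × 0.006229)/0.006218] = Φ(1.213) = 0.887.
- Both looks, no re-estimation: 0.891 by normal approximation, 0.898 by simulation.
- With re-estimation, assuming a promising-zone rule (lower conditional-power limit 0.30 to 0.50, target 0.90, cap 6000): 0.917 to 0.931. The actual rule is in the monitor's charter. The stated power above 0.90 reproduces on that assumption.

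**4. If 4% and 2% were nevertheless full 72-hour rates.** Suppose an equal share of strokes in each arm falls after discharge. The shares are assumed; re-estimation uses a lower limit of 0.36.

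| Share lost | Rates | No re-estimation (simulated) | With assumed re-estimation |
|---|---|---|---|
| 0% | 4.0 / 2.0% | 0.898 | 0.927 |
| 5% | 3.8 / 1.9% | 0.881 | 0.913 |
| 10% | 3.6 / 1.8% | 0.863 | 0.899 |
| 20% | 3.2 / 1.6% | 0.820 | 0.863 |

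The sign is not certain either. Section 5.1 says the filters come out after TAVR, so late strokes may be ones the device cannot affect. If each arm loses 0.2 points (3.8% versus 1.8%), two-look power by normal approximation rises from 0.891 to 0.910.

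**5. Whether the cited registry bounds the loss.** Section 4.1 gives 280 matched patients per group: stroke in 3.6% and 1.1% within 48 hours, and 4.6% and 1.4% overall. These are 10/280 and 3/280, then 13/280 and 4/280. The shares by 48 hours are 10/13 = 77% (exact 95% CI 46 to 95%) and 3/4 = 75% (19 to 99%). That is too imprecise to serve as a bound.

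**6. If discharge timing differed by arm.** True rate 3% in both arms, N = 3000, two looks, no re-estimation, normal approximation. The entry is the chance of declaring benefit.

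| Strokes missed | More missed in Test | More missed in Control |
|---|---|---|
| None | 0.025 | 0.025 |
| 12% versus 10% | 0.031 | 0.020 |
| 5% versus 0% | 0.043 | 0.014 |
| 10% versus 0% | 0.070 | 0.007 |

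The lower rows require loss in one arm and none in the other. Nothing in the documents supports that.

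**7. Whether a shorter fixed window would help.** If 50% to 90% of strokes occur by 24 hours (assumed), expected events are 30 versus 15, up to 54 versus 27. The 95% interval for the difference is then 0.13 to 1.87 points, or 0.64 to 2.96 points. Such an analysis recovers no stroke after discharge and moves further from 72 hours. It also assumes that nearly everyone is still in hospital at 24 hours, which the documents do not state.

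**The case for a change.** The best case for a change is that discharge is a post-randomisation decision by people who know the assignment, that ITT does not protect against unequal observation, and that a check chosen in advance is more credible than one added after the results. A table of time to discharge by arm would cost almost nothing.

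Part of this stands. The data support a statement about stroke in hospital up to 72 hours, and a report should say so. A by-arm description of time to discharge is good practice. The endpoint cannot be applied without discharge and stroke-onset times, so analysts will need those data and can tabulate them under the general descriptive provisions of Section 11.3. Section 11.3.5 allows the analysis plan to be amended before the analysis. Sections 11.1.1.1, 11.2 and 11.3.5 also point to a separate statistical analysis plan, and no such separate text was available for this review, so the absence of a check is established only for the text at hand.

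What does not stand is the step from a possible imbalance to a needed change. Each subject in either arm is to be examined by a neurology professional, with NIHSS and mRS, before leaving or by 72 hours, and the assessor should be blinded. That gives systematic in-person ascertainment up to the point where counting stops. Contacting early-discharged subjects at 72 hours would close the gap, but it adds follow-up and mixes remote with in-person assessment. Choosing the in-hospital window is a fair trade-off.

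**Conclusion.** No change to the plan is needed. The gap between the objective and the endpoint is one of wording: the two summary statements omit a limit that every operative statement includes, and harmonising them would alter nothing the trial counts, tests or concludes. The planning rates are, by the plan's own notation, rates of the to-discharge endpoint, so the early cut-off takes nothing from the stated power.

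The remaining risk is a difference in discharge timing between arms. Its size and direction are unknown. A small imbalance (12% versus 10% of strokes missed) moves the false-benefit rate from 2.5% to about 3.1% or 2.0%; larger distortions need one-sided losses for which the documents give no ground. A routine description of time to discharge by arm would show whether the question arises.

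This rests on reading P_Control and P_Sentinel as Section 11.1.1.1 defines them, and on assumed shares of stroke after discharge. If 4% and 2% were instead 72-hour rates, an equal 10% loss would put power at about 0.90 under the assumed re-estimation rule.

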#### 6.2.2. **Additional Measurements**

The additional measurements shown below are based on NeuroARC and Valve Academic Research Consortium (VARC) endpoints and definitions and will be assessed through 72 hours post TAVR procedure or discharge (whichever comes first). Mortality (cardiovascular and non-cardiovascular), neurological endpoints (stroke, transient ischemic attack [TIA], and delirium), acute kidney injury, and Sentinel access site major vascular complications will be adjudicated by an independent CEC.

- All-cause death (cardiovascular and non-cardiovascular)
- Neurological endpoints (see **Note 1** below)
  - Stroke (disabling and non-disabling)
  - Transient ischemic attack

- Delirium
- Safety composite of all-cause mortality and all stroke
- Neurological status as determined by the following (see **Note 1** below):
  - Neurological physical examination
  - Modified Rankin Scale (mRS) score
  - National Institutes of Health Stroke Scale (NIHSS)
  - Confusion Assessment Method for Intensive Care Unit Patients (CAM-ICU)
  - Montreal Cognitive Assessment (MoCA)
- Acute kidney injury based on the AKIN System^26 Stage 3 (including renal replacement therapy) and Stage 2
- Sentinel access site vascular complications related to the procedure (major and minor)
- Sentinel system acute delivery and retrieval (categorized as successful deployment of both filters, 1 filter, or no filter and retrieval of the system)
- Health status as evaluated by EQ-5D Quality of Life questionnaire at baseline

**Note 1:** The neurological physical examination must be carried out by a neurology professional (board certified/board eligible neurologist, neurology fellow, neurology physician assistant, or neurology nurse practitioner). The NIHSS, mRS, and MoCA must be performed by certified personnel. The CAM-ICU must be done by personnel with appropriate training as documented by the sponsor. In all subjects where stroke is suspected, a formal neurology/stroke consult should be obtained, and the subject should be further assessed and treated per standard of care. In subjects diagnosed with post-procedural stroke, mRS must also be administered 30±7 days following the stroke; the simplified mRS questionnaire may be used for this follow-up assessment.

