The pivotal multicenter SENTINEL RCT was larger (N=363) than the aforementioned RCTs and showed that Sentinel use during TAVR was safe with no increased procedural complications. Subjects were prospectively randomized 1:1:1 into a safety arm (N=123, Sentinel only) and 2 imaging cohorts (device arm [N=121] and control arm without Sentinel [N=119]). The primary safety endpoint was 30-day major adverse cardiac and

cerebrovascular events (MACCE; defined as all death, all stroke, and stage 3 acute kidney injury [AKI] per Valve Academic Research Consortium [VARC-2] definitions). Stroke occurrence was assessed by NIHSS and modified Rankin scale (mRS) score as administered by a neurologist. In the combined safety and device arms, the MACCE rate of 7.3% was non-inferior ( $P < 0.001$ ) to the prespecified performance goal of 18.3% and similar to the control rate (9.9%;  $P=0.41$ ). As Sentinel is a temporary accessory device, a post hoc analysis was performed to assess stroke at the time most applicable to device usage. The stroke rate at  $\leq 72$  hours was 3.0% in the combined safety and device arms compared to 8.2% in the control arm, demonstrating a relative reduction of 63% in stroke rates in favor of Sentinel. At 30 days, event rates for subjects with Sentinel were similar to rates in the control arm for mortality (1.3% vs. 1.8%, respectively,  $P=0.25$ ), stroke (5.6% vs. 9.1%,  $P=0.25$ ), stage 3 AKI (0.4% vs. 0.0%,  $P=1.00$ ), and major vascular complications (8.6% vs. 5.9%,  $P=0.53$ ).

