### 7.1. Scale and Duration

An initial enrollment of up to 3000 randomized subjects in up to 100 study centers is planned (see **Note 1** below). A single center may enroll up to 15% of the total enrollment; approval from the Sponsor is required for additional enrollment. Subjects to be treated via a transfemoral approach with a commercially available TAVR device will be randomized 1:1 into a Test cohort using the commercially available Sentinel or a Control cohort with no cerebral protection system. A subject who provides an ICF signed by the subject or the subject’s legally authorized representative is considered enrolled in the study upon randomization, which will occur at the index procedure prior to procedural puncture/incision. The study duration for each subject is expected to be through 72 hours or hospital discharge, whichever comes first. In subjects diagnosed with a stroke, mRS must be administered at 30±7 days after the stroke. For these subjects, study duration will be through 30±7 days post stroke.

**Note 1:** If sample size re-estimation is needed (see Section **11.1.1.2**), the planned maximum enrollment will be up to 6000 randomized subjects.

**Figure 7.1-1** summarizes the study design. The treating physician must be a trained, experienced Sentinel user. Every subject must be deemed treatable with the Sentinel device (have suitable anatomy per the Sentinel Instructions For Use [IFU]). All eligible subjects (see Section **8**) should be approached for participation in the trial.

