## 19. Safety Reporting

### 19.1. Reportable Events by Investigational Center to Boston Scientific

It is the responsibility of the investigator to assess and report to BSC any event that occurs in any of following categories:

- All serious adverse events (SAE)
- All device-related adverse events
- All device deficiencies
- Unanticipated adverse device effects (UADE)/unanticipated serious adverse device effects (USADE)
- All CEC events (see below)
- New findings/updates in relation to already reported events

When possible, the medical diagnosis should be reported as the Event Term instead of individual symptoms.

If it is unclear whether or not an event fits one of the above categories, or if the event cannot be isolated from the device or procedure, it should be submitted as an adverse event (AE) and/or device deficiency.

Any AE required by the protocol, experienced by the study subject after informed consent and once considered enrolled in the study, whether during or subsequent to the procedure, must be recorded in the eCRF. Collection of safety events includes all CEC events (see below), regardless of seriousness and device relationship.

Underlying diseases are not reported as AEs unless there is an increase in severity or frequency during the course of the investigation. Death should not be recorded as an AE but should only be reflected as an outcome of one (1) specific SAE (see **Table 19.2-1** for AE definitions).

Refer to the Instructions For Use for the known risks associated with the commercial device.

The endpoints (see endpoint definitions in **Table 25.2-1**) requiring adjudication by the CEC include the following.

- Death: cardiovascular and non-cardiovascular
- Stroke: disabling and non-disabling
- Transient ischemic attack
- Delirium
- Acute kidney injury (Stage 2 and Stage 3)
- Sentinel access site major vascular complications related to the procedure

Details on the CEC events and procedures are outlined in the CEC charter. Tests and images required to adjudicate these events are specified in the event definitions (see **Table 25.2-1**).

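### The only vascular safety measure is tied to an access site that Control subjects do not have, so no pre-specified or adjudicated vascular or bleeding comparison between arms is planned

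*Combined protocol and SAP*

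**What the plan says.** Table 6.3-1 gives as one objective "Evaluate safety of the cerebral protection device", to be met with assessments recommended by VARC and NeuroARC. Section 6.2.2 lists the measures. The one vascular item is "Sentinel access site vascular complications related to the procedure (major and minor"). The adjudication list in Section 19.1 has one vascular entry, "Sentinel access site major vascular complications related to the procedure". Bleeding is in neither list, and the named safety composite is death plus stroke.

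Section 5.1 describes the device as "percutaneously placed from the right radial or brachial artery over a 0.014-inch guidewire". Section 7.1 sets it against a "Control cohort with no cerebral protection system"; transfemoral TAVR access is common to both arms.

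Table 25.2-1 defines VARC major and minor vascular complications without restricting them to the Sentinel site (aortic dissection and rupture are included), and also defines the VARC bleeding grades.

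Section 19.1 makes all SAEs reportable. Table 10.1-1 sets the window from enrollment to 72 hours or discharge, and Section 11.1.2 says AE and SAE rates will be reported. Section 11.3.1 says the additional measurements are not driven by hypotheses.

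Section 4.1 reports from the pivotal Sentinel trial "major vascular complications (8.6% vs. 5.9"%, P=0.53), introduced by "At 30 days, event rates for subjects with Sentinel were similar to rates in the control arm".

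**The concern.** The randomized contrast is an added upper-limb arterial access, with filters placed in two arch vessels, against neither. The vascular measure chosen can count events only where the device was used. It therefore describes the Test arm and gives no randomized comparison. An aortic injury or a femoral-site complication falls outside it in both arms, so the listed measures cannot show whether such events are more frequent with Sentinel than with TAVR alone.

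Of the four 30-day outcomes that Section 4.1 compares in that sentence (mortality, stroke, stage 3 AKI, major vascular complications), the first three are adjudicated in both arms here. The fourth, which has the largest numerical difference against Sentinel, has no both-arm counterpart. A positive stroke result would then be published without a pre-specified randomized estimate of vascular or bleeding harm, in a trial far larger than any that its background cites.

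**Working it through.** **Step 1. Is there a comparator?** The listed measure needs a Sentinel access site. Test subjects have one at the right radial or brachial artery. Control subjects have none unless they cross over. Under ITT a crossover could contribute an event to Control, but that is not a meaningful contrast.

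**Step 2. What else captures vascular events in both arms?**
- SAEs are captured in both arms and their rates reported, but without adjudication or VARC grading.
- Table 19.4-1 has reporting lines for serious and non-serious VARC events, but the reportable categories in Section 19.1 do not include VARC events as a class.
- The definition of a CEC event in Table 25.2-1 names only mortality, stroke/TIA and delirium. It omits AKI and vascular complications, which Section 19.1 includes.

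Non-serious vascular events away from the Sentinel site are therefore not clearly captured.

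**Step 3. The background figure.** Section 4.1 gives randomized numbers of 123 and "device arm [N=121] and control arm without Sentinel [N=119"], that is 244 Sentinel and 119 control. Evaluable denominators are not given, so the counts are an assumption: 0.086 × 244 ≈ 21 and 0.059 × 119 ≈ 7.
- Difference: 21/244 − 7/119 = 2.7 points.
- SE = √(0.0861×0.9139/244 + 0.0588×0.9412/119) = 2.81 points; 95% CI −2.8 to 8.2.
- P = 0.36 (chi-square), 0.41 (Fisher), 0.48 (continuity-corrected).

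The stated 0.53 is not matched at these denominators. That is not evidence of an error, and every version is non-significant.

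**Step 4. What this trial could estimate.** Inputs: 1500 per arm (Section 11.1.1.2) and the background rates multiplied by a fraction f. The 8.6% and 5.9% are 30-day rates and this window ends at 72 hours or discharge, so f is unknown and is varied.
- CI: (p1 − p2) ± 1.96 × √[(p1q1 + p2q2)/1500].
- Power (two-sided 0.05): Φ{[(p1 − p2) − 1.96√(2p̄q̄/1500)] / √[(p1q1 + p2q2)/1500]}.

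| f | Rates | Difference (points) | SE (points) | 95% CI (points) | Power |
|---|---|---|---|---|---|
| 1 | 8.6% vs 5.9% | 2.70 | 0.946 | 0.8 to 4.6 | 81% |
| 0.75 | 6.45% vs 4.425% | 2.03 | 0.827 | 0.4 to 3.6 | 69% |
| 0.5 | 4.3% vs 2.95% | 1.35 | 0.682 | 0.0 to 2.7 | 51% |
| 0.25 | 2.15% vs 1.475% | 0.68 | 0.487 | −0.3 to 1.6 | 28% |

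At f = 0.5 the lower limit is 0.01 points; at f = 0.49 the interval already includes zero. If re-estimation takes the trial to 3000 per arm, f = 1 gives 98% power and a half-width of 1.3 points.

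**Step 5. Volume.** At f = 1, any-site major vascular events would number about 1500 × (0.086 + 0.059) ≈ 218. Expected primary strokes at 4% and 2% are 1500 × 0.06 = 90.

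**The case against.** The scope is a defensible choice. This is a post-market trial of an approved device with a stroke objective, no safety success criterion and no hypotheses on the additional measurements. Femoral access is common to both arms. Measuring the added access directly avoids that background, and with a structural zero in Control the Test rate is itself the excess at that site. This stands for the access site. It does not cover aortic injury or bleeding, where events can occur in both arms and only a contrast separates device from procedure.

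Three stronger readings are tempting, and the documents do not support them.

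- *That the trial cannot compare vascular safety at all.* SAEs are collected in both arms over the same window and their rates will be reported, so serious vascular events can be compared descriptively. What is missing is a pre-specified, VARC-graded measure.
- *That the background shows harm, or excess complications across all sites.* Section 4.1 calls the rates similar, gives P=0.53 and does not say which sites were counted. Nor do the documents give a reason for the narrower measure, so no motive should be read into it.
- *That this trial would settle the question.* That depends on carrying a non-significant 30-day difference into a window of at most 72 hours. At half the rates, power is about even.

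**Conclusion.** The gap is real but limited: no pre-specified or adjudicated any-site vascular or bleeding measure is compared between arms, despite a VARC-based safety objective and definitions already in the protocol. The primary analysis is unaffected. The gain from closing the gap is precision. The interval would be about 3.7 points wide at the full background rates and narrower at lower ones, against about 11 points in the pivotal trial. Whether it would exclude zero depends on the true difference and on the unknown share of events that fall in the shorter window. The widths assume 1500 evaluable per arm; the pivotal-trial interval also assumes randomized denominators. This is a cheap improvement worth making, not a contradiction that invalidates the plan.

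**What to change.** In Section 6.2.2, keep the Sentinel-site item as a description of the Test arm. Add two measures in both arms through 72 hours or discharge: VARC major vascular complications at any site, including aortic injury, and VARC life-threatening/disabling and major bleeding. Derive them by applying Table 25.2-1 to the SAEs already collected, with the Sentinel site as a labelled subset. Report the between-arm difference with a 95% CI and no hypothesis test. Specify the derivation in the statistical analysis plan before unblinding.

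Reconcile the reportable-event and adjudication lists in Section 19.1 with the VARC-event lines in Table 19.4-1 and the CEC-event definition in Table 25.2-1.

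The cost is one table and some classification work, with no added visit or procedure. The limits should be stated. The measure is unadjudicated, comes from operators who know the assignment, and misses events not reported as serious. Table 10.1-1 schedules no hemoglobin or transfusion data, so bleeding grades depend on what the SAE report records. Adjudicating any-site events would address the first two limits in part. It is optional: at the full background rates it could add up to about 218 vascular dossiers, plus bleeding dossiers that the documents give no rate to estimate.
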